Dose of administration	COVERSYL® (perindopril erbumine) 4 mg will be administered daily for 21 days of a 28-day cycle. Perindopril will be administered orally, first thing in the morning on an empty stomach. Regorafenib will be administered 160 mg daily for 21 days of a 28-day cycle. Regorafenib will be administered with low fat breakfast, one hour after perindopril. A low fat breakfast as defined by the Regorafenib monograph is one that is <30% fat, ~300-550 calories.
Route of administration	Both medications will be administered orally
Duration of treatment	
The study will be discontinued if 5 of the first 10 patients exhibit a Grade 3 or higher HFSR. Note that in the CORRECT trial, 47% of patients experienced HFSR of all grades with 17% experiencing HFSR with grade 3 severity.
 
Patients will remain on trial and will receive regorafenib and perindopril until radiological disease progression, based on RECIST v1.1 criteria. If patients progress on regorafenib, both drugs will be stopped. However, after the patient progresses (i.e. is no longer on trial) the medication can be continued if the investigator feels that there is a clinical benefit.
 
Other reasons for patients to discontinue therapy include: death; patient withdraws consent; treating physician determines

Phase II Study of Perindopril and Regorafenib in mCRC (PARICCA)

	discontinuation of treatment is in the patient's best interest; substantial non-compliance with the protocol.
Indication	
Patients with metastatic colorectal carcinoma (mCRC) who have progressed on/ after, or are intolerant to all approved drugs* for CRC and are eligible for regorafenib will be included in this trial.
 
*fluoropyrimidine-based chemotherapy, oxaliplatin, irinotecan, an anti-vascular endothelial growth factor (anti-VEGF) therapy, and, if RAS wild type, an anti-epidermal growth factor receptor (anti-EGFR) therapy.

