3.5 Location of laboratory and imaging facilities

[figure not shown]
The laboratory and imaging facilities for this study are both located on the 3rd floor of the BC Cancer Agency at [name].

4. Study design

Phase II, open-label, single-arm trial of patients with refractory mCRC treated with regorafenib (160 mg/day) and perindopril (4 mg/day).

This study will be conducted at the BC Cancer Agency (Vancouver Centre) only.

PARICCA trial design

Primary endpoint: Incidence of all grade toxicities for HFSR

Secondary endpoints: Incidence of (all grade) hypertension & toxicity; Severity of HFSR; Time course to development of worst grade (stage3) HFSR; Progression Free Survival.

Treat until progression, unacceptable toxicity, or withdrawal

During the study period, patients will undergo evaluations for safety and drug accountability every cycle. Drug safety will be monitored and evaluated continuously throughout the study, including a 30-day follow up period. Patients will continue on treatment until one of the following occurs (main criteria):

- Progressive Disease as defined by Response Evaluation Criteria in Solid Tumors (RECIST) criteria, version 1.1, or clinical progression
- Death
- Unacceptable toxicity
- Patient withdraws consent
- Treating physician determines discontinuation of treatment is in the patient's best interest
- Substantial non-compliance with the protocol

For the full list of criteria refer to section 5.2.1.

If in the Investigator's opinion, treatment with regorafenib is providing clinical benefit to a patient experiencing disease progression, the patient may continue treatment.

Justification of the design

47% of regorafenib treated patients in the CORRECT trial experienced HFSR of all grades, while 17% of regorafenib patients experienced grade 3 HFSR. All efforts need to be made to find new therapeutic combinations to reduce HFSR, as it causes a significant decrease in a patient's quality-of-life.

Although we are assuming that the co-administration of perindopril with regorafenib will mitigate HFSR symptoms, this may not be the case. If the HFSR is more severe with the addition of perindopril than with regorafenib alone, the study will be discontinued.

The choice of dosage and schedule to be used in this trial comes from data accumulated in previous phase III trials with regorafenib (CORRECT, CONCUR). The choice of dosage and schedule for perindopril is from the Coversyl monograph.

End of study

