5.2 Withdrawal of subjects from study

Patients will remain on trial and will receive regorafenib and perindopril until clinical radiological disease progression, based on RECIST v1.1 criteria. If patients progress on regorafenib, both drugs will be stopped. However, after the patient progresses (i.e. is no longer on trial) the medication can be continued if the investigator feels that there is a clinical benefit.

A subject may discontinue participation in this study at any time at the investigator's discretion or at the request of the subject.

If a subject discontinues before treatment starts (Cycle 1, day 1) she/he is not required to complete end of study assessments.

If a subject discontinues after receiving treatment for any reason, the investigator should make every effort to complete end of study assessment and the one month follow-up assessments of concomitant medications and adverse events.

Any occurrence of death, and any excluded medications taken after study withdrawal should be documented in the CRF and source documents.

Subjects withdrawn from the study retain their subject number, if already given. New subjects will be allocated a new subject number.

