7.1.2.3 End of Treatment Visit

When a patient is taken off treatment, the following assessments should be performed within 14 days (+/- 7 days) after study treatment has stopped:

- Brief medical history and complete physical examination including review of all organ systems, examination of pertinent organ systems, vital signs (heart rate, blood pressure and temperature) and weight
- ECOG performance status
- A CBC with differential should be performed: RBC, hemoglobin, hematocrit, platelet count and WBC. WBC must include differential neutrophil, lymphocyte, monocyte, basophil and eosinophil counts.
- Liver function tests
- CEA testing
- Creatinine
- Urinalysis: appearance, pH, glucose, ketones, erythrocytes, leukocyte esterase, nitrite, bilirubin, urobilinogen, protein, creatinine, and protein/creatinine ratio. A microscopic analysis should be performed if the appearance is turbid, or if protein, leukocytes, erythrocytes or nitrite are out of normal range.

Phase II Study of Perindopril and Regorafenib in mCRC (PARICCA)

- Quantification of proteinuria by urinary protein/creatinine ratio on a random urine sample preferably taken at mid-morning. This should be reported as the ratio of concentrations of total urine protein (in mg/dl) to urine creatinine (in g/dl).
- Measurement of GFR according to the MDRD (Modified diet in renal disease) abbreviated formula.
- 12-lead ECG
- Concomitant medications
- Toxicity and adverse events documentation
- For patients who discontinue for reasons other than disease progression, tumor measurements and evaluation of tumor response of all measurable lesions should be performed according to RECIST criteria, version 1.1.

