7.3 Efficacy

Phase II Study of Perindopril and Regorafenib in mCRC (PARICCA)

The primary endpoint of this trial is a safety endpoint. Efficacy measurement in this study will be assessed as a secondary endpoint, and will be measured by assessing progression-free survival (PFS). PFS will be evaluated based on RECIST v1.1 criteria, 20% progression or any new lesion.

Measurements will be made at baseline and then every 8 weeks during the treatment period until progressive disease is documented, and also at the end of treatment visit if applicable. At baseline, information on all potential sites of tumor lesions should be obtained, at a minimum patients must have a radiologic examination of chest, abdomen and pelvis. Throughout the study period, the same lesions to those identified and measured at baseline must be evaluated using the same technique, the identical contrast agent and the same slice thickness. If additional lesions are suspected, the relevant anatomical regions should be evaluated by appropriate radiologic examinations.

If a patient discontinues treatment prematurely before progression (e.g., due to toxicity), the investigator should perform a complete physical, laboratory and radiological assessment as soon as possible after study drug discontinuation. After treatment discontinuation, tumor assessments should be continued until progression, even if the patient receives other treatments.

For the purposes of defining progressive disease, every effort should be made to obtain radiographical imaging at the defined timepoints.

In cases where radiographic imaging is not possible, clinical progression may be used. Clinical progression is based on the judgment of the investigator.

The complete list of variables to be analyzed for this study will be provided in the statistical analysis plan.

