8.4.2 Progression-free survival

Progression-free survival is defined as the time (days) from start date of study drugs to date of first documented disease progression (radiological or clinical) or death due to any cause, if death occurs before progression is documented. The actual date that the tumor scan was performed will be used for this calculation. Progression-free survival for patients without disease progression or death at the time of the final analysis will be censored at the last date of tumor evaluation. Progression-free survival for patients who have no tumor assessments after baseline will be censored at 1 day. Missing or non-evaluable tumor assessments will not be taken into account in the calculation of PFS. Every effort will be made to obtain radiologic imaging for documentation of progression. In those cases where patients are unable to obtain radiologic examinations due to deterioration of medical condition, the date of clinical progression will be used for the determination of the date of progression. The PFS distribution will be presented descriptively using Kaplan-Meier curves. The median PFS from the Kaplan-Meier distribution will be determined along with the associated 95% confidence interval.

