an absolute increase of at least 5mm. Unequivocal progression of existing non-target lesions or the appearance of one or more new lesions will also constitute progressive disease.

Table 1: Response for patients with Target and Non-Target Lesions

Target Lesions	Non-Target Lesions	New Lesions	Overall Response	Best Response for this category also requires
CR	CR	No	CR	
CR	Non-CR/Non-PD	No	PR	
CR	Not evaluated	No	PR	
PR	Non-PD or not all evaluated	No	PR	
SD	Non-PD or not all evaluated	No	SD	documented at least 6 wk. from enrollment
Not all evaluated	Non-PD	No	NE	
PD	Any	Yes or No	PD	
Any	PD	Yes or No	PD	
Any	Any	Yes	PD	

Subjects with a global deterioration of health status requiring discontinuation of treatment without objective evidence of disease progression at that time should be reported as “*symptomatic deterioration*”. Every effort should be made to document the objective progression even after discontinuation of treatment.

Table 2: Response for patients with Non-Target Lesions only

Non-Target Lesions	New Lesions	Overall Response
CR	No	CR
Non-CR/Non-PD	No	Non-CR/non-PD*
Not evaluated	No	NE
Unequivocal PD	Yes or No	PD
Any	Yes	PD

* Non-CR/non-PD is preferred over “stable disease” for non-target disease.

Methods of Measurement

The same method of assessment and the same technique should be used to characterize each identified and reported lesion at baseline and during follow-up.

Clinical Lesions - Clinical lesions will only be considered measurable when they are superficial (e.g. skin nodules, palpable lymph nodes) and ≥ 10 mm diameter as assessed using calipers. For the case of skin lesions, documentation by colour photography including a ruler to estimate the size of the lesion is recommended.

Chest X-ray - Lesions on chest X-ray are acceptable as measurable lesions when they are clearly defined and surrounded by aerated lung. However, chest CT is preferable.

CT / MRI - CT is the best currently available and reproducible methods to measure target lesions selected for response assessment. CT scans should be performed with cuts of 5 mm or less in slice thickness. When CT scans have slice thickness greater than 5 mm, the minimum size for a measurable lesion should be twice the slice thickness. MRI is also acceptable. This applies to the chest, abdomen and pelvis. Head & neck and extremities usually require specific protocols.

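### The plan is inconsistent on clinical progression: the stopping passages disagree, and Section 8.4.2 leaves two groups of unscanned patients without a single PFS status

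*Combined protocol and SAP*

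**What the plan says.** **Stopping treatment**

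- Section 4 gives as its first stopping reason "Progressive Disease as defined by Response Evaluation Criteria in Solid Tumors (RECIST) criteria, version 1.1, or clinical progression", with no imaging condition.
- The Synopsis (Duration of treatment) continues both drugs "until radiological disease progression, based on RECIST v1.1 criteria". Its other reasons include the physician's best-interest decision, but not clinical progression.
- Section 5.2 reads "until clinical radiological disease progression, based on RECIST v1.1 criteria", which could mean either kind of progression or both together.
- Section 5.2.1, which Section 4 calls the full list, gives disease progression with no qualifier. It neither names nor excludes clinical progression.

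**PFS**

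- Section 8.4.2 measures PFS to the "date of first documented disease progression (radiological or clinical) or death due to any cause".
- The same paragraph gives the clinical date to patients who cannot be scanned because their condition has deteriorated. Patients without progression or death are censored at the last tumour evaluation. Patients with no tumour assessment after baseline are censored at day 1.
- Sections 7.3 and 8.1 and the Synopsis statistical text say: "In cases where radiographic imaging is not possible, clinical progression may be used".
- Sections 2.2 and 7.3 also contain a sentence describing PFS by RECIST alone.
- Appendix 14.1 has a separate category, symptomatic deterioration, for decline without objective progression: "Subjects with a global deterioration of health status requiring discontinuation of treatment without objective evidence of disease progression at that time should be reported as" that category. It then asks that objective progression still be sought after treatment ends.

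**End-of-treatment scan**

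- Section 7.1.2.3 states: "For patients who discontinue for reasons other than disease progression, tumor measurements and evaluation of tumor response of all measurable lesions should be performed". It does not say whether a stop for clinical progression counts as disease progression.

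**The concern.** A patient taken off treatment because of clinical decline is among those most likely to be progressing. Censoring such a patient removes someone at high risk from the Kaplan-Meier risk set without recording an event. That is informative censoring, and it biases PFS upward. Whether it happens here depends on which sentence the analyst applies.

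PFS is the trial's only efficacy measure (Section 7.3), scans are eight weeks apart, and clinical progression is an open-label investigator judgement. The rule should therefore be fixed before the data are seen.

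**Working it through.** **Which patients are settled.** Take a patient who stops for clinical progression with no scan at that time.

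| Patient | Sentences that apply | PFS status |
|---|---|---|
| Cannot be scanned; has at least one post-baseline scan | 8.4.2 event definition and its clinical-date sentence | Event on the clinical date: settled |
| Could be scanned but was not; has at least one post-baseline scan | 8.4.2 event definition, against the inability condition in 8.4.2, 7.3 and 8.1 and the RECIST-only sentences in 2.2 and 7.3 | Event on the clinical date, or not an event then (censored at the last scan unless progression or death follows) |
| Clinical progression before any post-baseline scan | 8.4.2 event definition, against 8.4.2 day-1 censoring | Event on the clinical date, or censored at day 1 |

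The third row is a conflict within a single paragraph. The day-1 sentence states no exception for clinical progression, nor for death.

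**Size.** The plan states no PFS sample size, power or target to reproduce; the 34 patients and 80% power concern HFSR only.

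*Inputs from the documents:* scans every 8 weeks (56 days; 7.1.2.2 and 7.3), and reference median PFS on regorafenib of 1.9 and 3.2 months (1.6). At 30.4375 days per month these are about 58 and 97 days.

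*Assumptions:* exponential time to progression, and a share f of progressions that are called clinically before the next scan and not scanned. The documents give no value for f, so 10%, 20% and 30% are shown.

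Let S1 be the probability of being progression-free at day 56, and F1 = 1 − S1.

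- Median 58 days: S1 = exp(−ln 2 × 56/58) = 0.512; F1 = 0.488.
- Median 97 days: S1 = exp(−ln 2 × 56/97) = 0.670; F1 = 0.330.

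Three estimates of PFS at day 112 (16 weeks):

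1. Every clinical progression is an event: S1². This is 0.262 or 0.449.
2. Day-1 rule only. A fraction f × F1 leaves the risk set at day 1 and everyone else is counted: S1² / (1 − f × F1). Example at 58 days, f = 20%: 0.262 / (1 − 0.2 × 0.488) = 0.262 / 0.902 = 0.291.
3. Every clinical progression is censored at the last scan, or at day 1 if there is none. Survival past day 56 becomes S1 / (1 − f × F1). With a constant hazard the same ratio applies to the second interval, giving [S1 / (1 − f × F1)]². Same example: (0.512 / 0.902)² = 0.322.

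| True median | f | All counted | Day-1 rule only | All censored (upper bound) |
|---|---|---|---|---|
| 58 days | 10% | 26.2% | 27.6% | 29.0% |
| 58 days | 20% | 26.2% | 29.1% | 32.2% |
| 58 days | 30% | 26.2% | 30.7% | 36.0% |
| 97 days | 10% | 44.9% | 46.4% | 48.0% |
| 97 days | 20% | 44.9% | 48.1% | 51.5% |
| 97 days | 30% | 44.9% | 49.8% | 55.3% |

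The day-1 rule alone adds 1.3 to 4.9 points. The upper bound adds about 3, 6 to 7, and 10 points at the three shares. F1 is also the fraction of clinical progressions that precede week 8: about a half (58 days) or a third (97 days).

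**The case against.** The best defence is that Sections 8.4.2, 7.3 and 8.1 and the Synopsis share one hierarchy: image first, and use the clinical date if imaging cannot be done. That is correct, and it settles the first row of the table of patients. It rules out some stronger readings that a reader might infer:

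- *That 8.4.2 counts clinical progression without restriction and so contradicts 7.3 and 8.1.* Its event definition is broad, but its later sentence ties the clinical date to inability to be scanned.
- *That 5.2.1 excludes clinical progression.* It is silent. Its mention of RECIST concerns patients who continue treatment after progression.
- *That patients stopped for clinical progression are exempt from the end-of-treatment scan.* This rests on an undefined term. If disease progression in 7.1.2.3 means RECIST progression, these patients are to be scanned. Section 7.3 and Appendix 14.1 also ask for every effort to image.
- *That PFS is inflated by 6 to 10 points.* This treats every clinical progression at a 20% or 30% share as ambiguous. If only half of a 20% share could have been scanned but were not, the 10% rows apply and the bound is about 3 points. A scan at the next scheduled time would close the week-16 gap. A later death would also be an event, since 8.4.2 censors at the last evaluation only patients without progression or death.

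It is also fair that PFS has no test, comparator or decision rule.

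The defence does not reach the day-1 conflict, where following one sentence of 8.4.2 breaks another. Nor does it cover the patient who could have been scanned but was not: a request for every effort does not say how to classify a scan that was never done.

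**Conclusion.** The concern holds in limited form. Section 4 and the Synopsis conflict on clinical progression as a stopping reason, and 5.2 is unclear. For PFS, two groups lack a single status: patients stopped clinically who could have been scanned but were not, and patients with clinical progression before the first post-baseline scan.

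Following the day-1 rule as written would raise 16-week PFS by about 3 points at an assumed 20% clinical share, and by roughly 1 to 5 points across 10% to 30%. Censoring every clinical progression is an upper bound of about 3 to 10 points, not an expected effect. These figures rest on exponential PFS, the two reference medians, an assumed clinical share, and no scan being taken at the clinical stop. The HFSR analysis is unaffected. The change is worth making because it is cheap and PFS is the only efficacy measure, but the trial's main conclusion does not depend on it.

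**What to change.** 1. Reconcile the stopping wording in the Synopsis and Sections 4, 5.2 and 5.2.1, and define disease progression as used in 7.1.2.3. The choice of rule belongs to the sponsor.
2. In 8.4.2, state that documented clinical progression without a scan is a PFS event on its date, and that clinical progression, like death, overrides the day-1 censoring rule. Keep the text that puts imaging ahead of clinical judgement. Align 2.2, 7.3, 8.1 and the Synopsis statistical text.
3. Add one sensitivity Kaplan-Meier analysis that counts only radiological progression and death as events.

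The cost is wording edits and one extra curve. The reported PFS may be slightly less favourable than under day-1 censoring.

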5.1 Eligibility

Patients with metastatic colorectal cancer (mCRC) who have progressed on/after all approved drugs for CRC and are eligible for regorafenib. Specifically, regorafenib is indicated for the treatment of patients with metastatic colorectal cancer (mCRC) who have been previously treated with fluoropyrimidine-based chemotherapy, oxaliplatin, irinotecan, an anti-VEGF therapy, and, if *KRAS* wild type, an anti-EGFR therapy (*Stivarga*® (*regorafenib*) *Product Monograph*).

Patients will have been tested for Ras (K- and N- mutations).

5.1.1 Inclusion criteria

In order to be eligible, all inclusion criteria must be met.

A patient must:

- Understand, be willing to give consent, and sign a written informed consent form prior to undergoing any study-specific procedure
- Be male or female and ≥ 18 years of age
- Histological or cytological documentation of adenocarcinoma of the colon or rectum.
- Patients with metastatic colorectal cancer (Stage IV) previously treated with fluoropyrimidine-based chemotherapy, oxaliplatin, irinotecan, an anti-VEGF therapy, and, if *KRAS* wild type, an anti-EGFR therapy.

Phase II Study of Perindopril and Regorafenib in mCRC (PARICCA)

- Progression during or within 3 months following the last administration of approved standard therapies, or have experienced intolerance to previous therapy. Patients treated with oxaliplatin in an adjuvant setting should have progressed during or within 6 months of completion of adjuvant therapy. (Please note that in Canada patients are not re-challenged with oxaliplatin in the metastatic setting).
- Metastatic CRC patients with measurable or non-measurable disease
- Life expectancy of at least 3 months
- Have an Eastern Cooperative Oncology Group performance status of 0 or 1 (within 14 days prior to the initiation of study treatment)
- Have adequate bone marrow, liver function, and renal function as measured by the following laboratory assessments conducted within 7 days prior to the initiation of study treatment:
 - Total bilirubin \leq 1.5 times the upper limit of normal (ULN)
 - Alanine aminotransferase (ALT) and aspartate aminotransferase (AST) \leq 2.5 times the ULN ($<$ 5 times ULN for patients with liver involvement of their cancer)
 - Lipase \leq 1.5 times the ULN
 - Serum creatinine \leq 1.5 times the ULN
 - Glomerular filtration rate \geq 30 mL/min/1.73 m² according to the modified diet in renal disease abbreviated formula
 - International normalized ratio (INR) of prothrombin time (PT; PT-INR) and partial thromboplastin time (PTT) \leq 1.5 times the ULN
 - Platelet count \geq 100000 /mm³, hemoglobin (\geq 9 g/dL, absolute neutrophil count \geq 1500/mm³).
 - Alkaline phosphatase limit \leq 2.5 times the ULN ($<$ 5 times ULN for patients with liver involvement of their cancer)
- If female and of childbearing potential, have a NEGATIVE result on a pregnancy test performed a maximum of 7 days before initiation of study treatment
- If female and of childbearing potential or if male, must agree to use adequate contraception (e.g., abstinence, intrauterine device, oral contraceptive, or double-barrier method) based on the judgment of the investigator or a designated associate from the date on which the ICF is signed until 6 months after the last dose of study drug.

